## **8.0 STATISTICAL METHODS**

### **8.1 Sample Size Considerations**

This study will identify patient characteristics at the time of the baseline imaging study that are predictive of an imaging study positive for M1 in patients with CRPC and no known M1. A minimum of 2000 patients will be registered in this study. This sample size is based on the following considerations.

The primary endpoint for the study will be the occurrence of a positive imaging study for M1 at baseline (yes or no), a binary variable. All patients with a baseline imaging study will be included in the analysis of the primary endpoint. Yu et al (2012) found that 32% of 2577 men screened for a trial enrolling patients with CRPC thought to be M0 did, in fact, have M1 CRPC, and it is anticipated that this study will have a similar finding. With 1000 patients at each of the 2 possible levels of a binary variable, for a total of 2000 patients, the variable is detectable with an odds ratio of 1.312 with 80% power using a 2-sided test at alpha = 0.05, assuming an imaging study positive for M1 at baseline in 34.95% and 29.05% of patients in level 1 and level 2 of the binary variable, respectively. However, a binary variable that is distributed at a ratio of 1:5 at baseline would allow for an odds ratio of 1.422 to be detected with 80% power assuming an imaging study positive for M1 at baseline in 38.5% and 30.6% of the patients in level 1 and level 2 of the binary variable, respectively.

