## **8.3 Analysis of Endpoints**

### **8.3.1 Primary Endpoint**

The primary endpoint for the study will be the occurrence of an imaging study at baseline that is positive for M1 (yes or no) among all patients enrolled with a baseline imaging study.

Logistic regression analyses will be used to analyze the primary endpoint. Univariate logistic regression analyses will be performed separately for each variable of interest. A multivariate logistic regression analysis will be performed including all variables of interest. A stepwise regression model selection procedure will be used to identify a model that includes explanatory factors that are independently predictive of the occurrence of a positive imaging study. The logistic regression model will be used to develop a formula for predicting the probability of a positive imaging study given specific values for the variables included in the final model.

Variables that will be considered for inclusion in the model are age, race, ethnicity, duration of disease in years from initial diagnosis to study registration, total Gleason score at diagnosis, post-RP Gleason score total, baseline ECOG performance status, baseline hemoglobin, baseline alkaline phosphatase, baseline LDH, baseline serum albumin, baseline testosterone, baseline serum PSA, baseline PSADT, first serum PSA demonstrating CRPC, baseline body mass index (BMI), prior systemic therapy (yes or no), prior ADT (yes or no), prior RP (yes or no), and prior orchiectomy (yes or no), current opioid analgesic use (yes/no), and number of prior scans. Baseline BPI scores, including worst pain in last 24 hours, least pain in last 24 hours, average pain in last 24 hours, and pain right now, will also be considered for inclusion.

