The above list of variables will be considered for inclusion in the final model; however, each variable will be initially screened and will be dropped from consideration for inclusion in the final model if it is shown to have little predictive value as a univariate predictor. Candidate variables for the final model will be determined by the following algorithm. A univariate logistic regression will be applied for each individual variable and all variables with  $p < 0.25$  will be considered as candidate variables for the final model. Interaction terms will also be considered for the final model. Interaction terms will be considered as candidates for the final model if the  $p$ -value for the interaction term is less than 0.25 from a model with predictor variables of variable a, variable b, and interaction of variable a and b. Only variables with  $p < 0.25$  from the univariate model screening procedure as discussed above will be considered for determining the list of interaction terms for consideration in the final model.

All candidate variables, including interaction terms identified by the algorithm discussed above, will be entered into the stepwise model selection procedure. The criteria for a variable to enter the model will be  $p < 0.05$  and variables will be retained in the model during the elimination step if  $p < 0.10$ . The final model will include all terms identified from the stepwise selection procedure and will also include all main effect terms for any interaction variables identified in the stepwise model selection procedure.

Although the above list of variables for consideration for inclusion in the model is a comprehensive one, addition or deletion of variables for consideration may occur. Therefore, the complete list of candidate variables for inclusion in the model will be provided in the final statistical analysis plan.

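### Stepwise selection for the primary model does not enforce hierarchy, so the final model is likely to report spurious interactions, and which ones depends on the origin and coding of the variables

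*Combined protocol and SAP*

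**What the plan says.** Protocol section 8.3.1 builds the primary logistic model in four steps.

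1. Each variable is screened alone and kept if p < 0.25.
2. For pairs of surviving variables, the product is kept as a candidate if p < 0.25 in a model that also holds both main effects.
3. "All candidate variables, including interaction terms identified by the algorithm discussed above, will be entered into the stepwise model selection procedure". A term enters at p < 0.05 and stays at p < 0.10.
4. The final model takes the selected terms and "will also include all main effect terms for any interaction variables identified in the stepwise model selection procedure".

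The section sets no hierarchy condition in step 3, no re-test of a product after step 4, and no centring or coding rule. The resulting model is meant to identify independent predictors and to supply the prediction formula. Section 8.3.2 uses similar analyses for the secondary endpoint.

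Section 8.3.1 leaves only the list of candidate variables to the final SAP. The closing page of the combined document says that the SAP was not finalized, so no later text settles the algorithm.

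**The concern.** Step 2 tests interaction properly, with both main effects present. Step 3 gives that up by letting products and main effects compete as equals. The add-back in step 4 has work to do only if a product can be selected without its main effects.

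The p-value of a product whose main effects are absent does not test interaction. For positive variables whose mean is large relative to their SD, the product is close to a weighted sum of the two variables. It can then enter because one or both main effects are real.

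At stake is the reading of the primary result. The model could report effect modification that does not exist, through terms that fail the plan's own retention threshold once their main effects are restored. Which terms appear would also depend on a coding choice that the plan does not state.

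**Working it through.** **Inputs from the plan.**
- Section 8.1: "A minimum of 2000 patients will be registered in this study". A cited screening series found 32% with M1, and "it is anticipated that this study will have a similar finding". That gives 0.32 × 2000 = 640 events.
- Section 8.3.1: 22 listed variables plus 4 BPI scores = 26 candidates, hence 26 × 25 / 2 = 325 possible pairs.

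**The plan's own figure.** Section 8.1 claims an "odds ratio of 1.312 with 80% power using a 2-sided test at alpha = 0.05", from 34.95% and 29.05% with 1000 men per level.
- Odds ratio: (0.3495/0.6505) / (0.2905/0.7095) = 1.312.
- Power: Φ[(0.059 − 1.96 × √(2 × 0.32 × 0.68/1000)) / √((0.3495 × 0.6505 + 0.2905 × 0.7095)/1000)] = Φ[(0.0590 − 0.0409)/0.0208] = Φ(0.87) = 0.81.
- The 1:5 case (38.5% and 30.6%) gives an odds ratio of 1.420 from the rounded rates, against 1.422 stated, and power 0.798.

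The sample size reproduces. The plan gives no figure for false interactions, so that part needs simulation.

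**Why origin matters and scale does not.**
- Rescaling: (ka)(mb) = km·ab. The coefficient is divided by km and the p-value is unchanged.
- Shifting: (a + c)(b + d) = ab + d·a + c·b + cd. This mixes main effects into the product. If a and b are not in the model, the test changes.
- In SD units, for independent a and b with means μ, ab = μ_b·a + μ_a·b − μ_a·μ_b + (a − μ_a)(b − μ_b). Only the last term is interaction. Its share of the variance is 1/(μ_a² + μ_b² + 1): 1/33 = 3% with both means 4 SD above zero, and 1/129 = 0.8% at 8 SD.

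**Simulation 1: six predictors.** n = 2000, about 32% positive, independent predictors, four real (odds ratio 1.22 per SD) and two noise, no interaction, means 4 to 8 SD above zero. All steps of section 8.3.1 were applied, including the p < 0.25 screens. Four runs:

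| Data sets | ≥1 false interaction, as written | Hierarchy enforced | As written, but centred |
|---|---|---|---|
| 200 | 83% | 25% | 31% |
| 200 | 88% | 29% | 36% |
| 100 | 80% | 28% | not reported |
| 100 | 84% | 23% | 31% |

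The simulation standard error of the as-written column is about 2 to 4 points, for example √(0.84 × 0.16/100) = 3.7 points. In the three runs that recorded it, 77–83% of the selected products had p > 0.05 once main effects were restored. In the run that tested coding, rescaling changed the selection in 0% of data sets and centring in 79%. With means only 1 to 2 SD above zero, the as-written rate was still 70–80%.

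**Simulation 2: all 26 candidates.** 16 continuous and 10 binary, n = 2000, 32% positive, no interaction, 120 data sets per setting. Ranges cover a common correlation of 0 to 0.2. The eight true main effects are log odds ratios of 0.25 per SD for six continuous and 0.4 for two binary variables.

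| | Eight true main effects | No true predictor |
|---|---|---|
| Mean false interactions, as written | 5.4–6.5 | 1.0–1.3 |
| Models with ≥1, as written | 100% | 62–66% |
| Selected with a main effect missing (mean) | 5.4–6.4 | 1.0–1.3 |
| p ≥ 0.10 after main effects restored (mean) | 2.8–3.0 | 0.5–0.7 |
| Mean false interactions, hierarchy | 1.56 | 0.02–0.05 |
| Models with ≥1, hierarchy | 79–80% | 2–5% |
| Selection changed by rescaling, as written | 0% | 0% |
| Selection changed by centring, as written | 100% | 60–74% |
| Selection changed by centring, hierarchy | 0% | 0% |

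The 1.56 left under hierarchy is about what multiplicity alone would give: eight main effects form 28 pairs, and 28 × 0.05 = 1.4. Centring without hierarchy is not a remedy: with eight true effects the mean was 4.9 at correlation 0 and 11.7 at correlation 0.2, against 5.4 and 6.5 uncentred.

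**The case against.** The strongest reply has five parts.

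- **The study is descriptive.** Section 8.2.2 says that no formal hypotheses are tested, and interactions are not a stated objective. The endpoint, the population, the univariate analyses and the full model with all variables are untouched. This stands and lowers the severity. It excuses unadjusted testing, but not a primary model that depends on unstated coding.
- **The interaction screen holds both main effects.** True, but every simulation applied that screen and it did not prevent the problem.
- **The add-back lets a reader see weak products.** This stands in part. With main effects restored, a product's test no longer depends on origin, and many products will show as non-significant. They are still in the reported model.
- **The prediction formula may be unharmed.** In one run of the six-predictor setting, AUC in 20,000 new patients was 0.603 as written and 0.604 with hierarchy. A reader might infer that the formula predicts worse; the evidence does not show that. Calibration was not examined.
- **Software might impose hierarchy.** The protocol names no such option, and under enforced hierarchy the add-back would be redundant.

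A reader might also infer that a change of units, such as years to months, alters the selected terms. It does not. Only a shift of origin or a change of coding does, such as centring or 0/1 versus 1/2.

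**Conclusion.** The procedure is wrong as written and should be fixed. Without hierarchy during selection, the primary model is likely to report interactions that do not exist, and their identity depends on the origin and coding of the variables.

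A reader might go further and say that the model is certain to contain false interactions. The documents do not support that. They give no effect sizes, means, SDs or correlations for the predictors, and the as-written rate ran from 62% to 100% across the assumed settings. The direction was the same in every comparison with enforced hierarchy.

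Nor does hierarchy cure the problem. With 26 candidates and real main effects, about 80% of models still hold at least one false interaction, although the mean count falls roughly fourfold (5.4/1.56 = 3.5; 6.5/1.56 = 4.2). The damage shown is to interpretation of the primary model.

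**What to change.** In section 8.3.1, replace the clause that adds main effects after selection with:

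> Hierarchy is enforced at every step: an interaction may enter only if both its main effects are in the model, and a main effect may not leave while an interaction containing it remains. Continuous variables are centred and coding is stated.

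The add-back clause should go only if this rule replaces it. Under hierarchy, centring no longer affects which products are selected; stating it fixes the meaning of the main-effect coefficients.

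The cost is one sentence and one software setting. A pure crossover interaction without main effects becomes less likely to be found. The change does not deal with testing up to 325 products unadjusted; a short pre-specified list of interactions and internal validation of the formula would address that separately.

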### **8.3.2 Secondary Endpoints**

The proportion of patients who receive a diagnosis of M1 CRPC at the time of the baseline imaging study will be categorized as metastatic due to soft tissue (nodal and/or visceral) metastases, bone metastases, or both. The percentage of patients in each category will be computed based on the primary analysis population.

Logistic regression analyses, similar to the analyses described for the primary endpoint, will be used to identify characteristics predictive of an imaging study positive for M1 in the M0 population. Analyses will be performed using baseline information only as predictor variables with the outcome variable as a positive imaging study (yes/no) at any post-baseline time point. In addition, an analysis will be performed on the M0 population using all imaging studies collected in the study as the outcome variable (positive=yes/negative=no) with predictor variables associated with each imaging study. Appropriate methods accounting for the correlation of multiple studies for a patient, such as generalized estimating equations, will be used for this analysis. Cox regression analyses incorporating information on the time to occurrence of a positive imaging study will be performed to supplement these analyses.

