Although serum PSA and PSADT have been shown to convey the relative risk of developing M1 disease (Smith 2005), other biomarkers may more accurately predict a positive imaging study (Brown 2010). Interactions between blood cells and distant metastatic cells may alter the gene expression profiles of circulating cells (Ross 2012). Recent studies have shown gene expression profiling of blood cells offers a minimally invasive approach that may be prognostic for OS and the various prostate cancer disease states, including development of M1 CRPC (Olmos 2012). Therefore, as additional optional research (AOR) in this study, blood samples will be collected at baseline and each M0 Phase visit to explore changes in gene expression profiles and their correlation with development of M1 disease.

The primary purpose of this research is to describe patient characteristics predictive of an imaging study positive for M1 in the population of patients with CRPC and no known M1. These data will contribute to clinical guidance regarding the timing and utility of imaging studies in patients with CRPC.

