### M0 Phase

During the M0 Phase, there are 2 types of visits. Post-baseline imaging studies are not required in the M0 Phase and are performed if the investigator determines imaging study(ies) is/are needed to assess development of metastases (M1 CRPC). Depending on the timing of an imaging study, its results may be recorded as part of the 6-month M0 Phase study visit or part of an M0 Phase imaging visit, as described below:

- **6-month M0 Phase study visit:** A scheduled 6-month M0 Phase study visit (office visit), will occur every 6 months ( $\pm$  1 month), starting from the date of the patient's registration, until 3 years after the last patient is registered. Any imaging study that occurs within 1 month of a 6-month M0 Phase study visit will be considered part of that 6-month M0 Phase study visit, and no repeat study assessments will be required.
- **M0 Phase imaging visit:** This visit occurs if, outside of the 1-month window for the 6-month M0 Phase study visit, the investigator determines imaging study(ies) is/are needed to assess development of metastases (M1 CRPC).

The choice of imaging modality will depend on the study site's standard of care; the same modality should be used for all images for a given patient until diagnosis of M1 CRPC. However, if the modality is changed to one with greater sensitivity (e.g., Tc 99m to NaF PET/CT or MRI) and diagnosis of M1 CRPC occurs at first use of a new imaging modality, an additional imaging study with the previous modality will be performed within 1 month after the positive imaging study; this additional imaging study will be reimbursed by the sponsor. However, if the modality is changed to one with lower sensitivity, an imaging study with the previous higher modality will not be performed.

Assessments for both types of M0 Phase visits include: ECOG performance status, current opioid analgesic use (yes/no), pain status (with BPI), prostate cancer interventions since the previous visit, survival status, blood samples for clinical laboratory tests (alkaline

phosphatase, hemoglobin, LDH, serum albumin, and serum PSA) and for AOR (if patient has consented to AOR), and safety events (serious adverse events [SAEs], see Safety Measures, below); all such data that have become available since the previous visit will also be collected.

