### **8.2 General Considerations**

#### **8.2.1 Analysis Populations**

The all-enrolled population will include all patients registered in the study. The primary analysis will be based on the primary analysis population, which will include patients in the all-enrolled population who undergo a baseline imaging study. In addition, patients with M0 or M1 CRPC at baseline (M0 or M1 populations, respectively) will form separate analysis populations to address different questions of interest.

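### The future-M1 analysis in Section 8.3.2 leads with a yes/no model without time at risk, and its scan-level model, as written, takes in baseline scans that cannot be positive

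*Combined protocol and SAP*

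**What the plan says.** Section 3.2 sets the secondary objective: find characteristics that predict a later scan positive for M1 in men who are M0 at baseline. Section 8.3.2 of the protocol answers it in three steps.

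- A patient-level logistic regression comes first, "using baseline information only as predictor variables with the outcome variable as a positive imaging study (yes/no) at any post-baseline time point".
- A scan-level analysis of the M0 population follows, "using all imaging studies collected in the study as the outcome variable", "with predictor variables associated with each imaging study", with a method such as generalized estimating equations for the within-patient correlation.
- Last, "Cox regression analyses incorporating information on the time to occurrence of a positive imaging study will be performed to supplement these analyses".

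The logistic work is described as similar to that for the primary endpoint, where Section 8.3.1 uses the model to "develop a formula for predicting the probability of a positive imaging study". Section 8.2.1 says "patients with M0 or M1 CRPC at baseline (M0 or M1 populations, respectively) will form separate analysis populations", so every man in the M0 population has a negative baseline scan.

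On follow-up, Section 4.0 (M0 Phase) says "Post-baseline imaging studies are not required in the M0 Phase and are performed if the investigator determines" a need. Section 7.3 ends M0 visits 3 years after the last registration, and Section 4.0 plans 2 years of accrual. Section 5.3 allows earlier withdrawal. On purpose, Section 1.2 states: "These data will contribute to clinical guidance regarding the timing and utility of imaging studies in patients with CRPC". The last page of the combined document records that the SAP was not finalized, so no later text adds detail.

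**The concern.** A yes/no outcome at any later time treats a man followed for 5 years and a man who died after 6 months alike if neither had a positive scan. A factor that shortens life, shortens follow-up or changes how often a man is scanned can therefore look protective or harmful without any effect on metastasis, and a true M1 predictor that also predicts death can be hidden. The candidate list in Section 8.3.1 includes age, performance status, hemoglobin, LDH and albumin, which could plausibly relate to death. It also includes PSA and PSADT, which Section 1.2 says clinicians use to decide when to scan.

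The scan-level model has a separate problem. If baseline scans are in the data set, about 1,360 records sit at time zero with an outcome that is fixed at negative. Any per-scan predictor that rises or falls over time then separates baseline scans from later ones and appears to predict positivity.

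At stake are the list of predictors, their effect sizes and any predicted probability used to advise on when to image.

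**Working it through.** The plan gives no sample size, power or event rate for this analysis, so there is no stated figure to reproduce. The sizes below are illustrations.

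**Inputs from the documents.** 2,000 men with 32% M1 at baseline (Section 8.1) leaves 2,000 × 0.68 = 1,360 in the M0 population. Planned M0 follow-up is 3 to 3 + 2 = 5 years.

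**Assumed.** M1 rate h = 0.2/yr (range 0.1–0.3), death 0.06/yr (range 0.03–0.10), dropout 0.03/yr, scans at random times at s = 1/yr, M1 found at the first scan after onset, binary factor split 1:1.

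**Step 1: no horizon.** Let L be the death plus dropout rate. The probability of a positive scan by time t is

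F(t) = [hs/(s−h)] × {[1−e^(−(h+L)t)]/(h+L) − [1−e^(−(s+L)t)]/(s+L)}.

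With h = 0.2, s = 1, L = 0.09, the leading factor is 0.25.
- 3 years: 0.25 × (2.004 − 0.883) = 28%.
- 5 years: 0.25 × (2.639 − 0.913) = 43%.
- At h = 0.1 the pair is 16% and 26%; at h = 0.3 it is 38% and 55%.

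A formula for the probability of a positive scan therefore means little without a time attached.

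**Step 2: factor linked to death, no effect on M1.** At the mean follow-up of 4 years:
- Reference, L = 0.09: 0.25 × (2.367 − 0.906) = 36.5%.
- Death HR 1.3, L = 0.108: 35.2%, OR 0.94.
- Death HR 2, L = 0.15: 32.3%, OR 0.83.
- Death HR 3, L = 0.21: 0.25 × (1.966 − 0.820) = 28.65%, OR = (0.2865/0.7135)/(0.3654/0.6346) = 0.70.

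Over the assumed M1 and death ranges, the OR at death HR 2 runs from 0.92 to 0.72.

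**Step 3: patient-level simulation** (1,360 men, follow-up uniform on 3–5 years, 2,000 runs). Entries are OR or HR, with the rejection rate at two-sided 5%.

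| Setting | Logistic, never scanned = no | Logistic, scanned men | Cox to end of M0 follow-up | Cox to last negative scan |
|---|---|---|---|---|
| No links | 1.00 (5–6%) | 1.00 (5–6%) | 1.00 (5–6%) | 1.00 (5–6%) |
| Death HR 2 | 0.83 (38%) | 0.89 (18%) | 1.00 (6%) | 1.04 (7%) |
| Death HR 3 | 0.70 (87%) | 0.79 (48%) | 1.00 (5%) | 1.08 (13%) |
| True M1 HR 1.5, death HR 3 | 1.06 (8%) | 1.27 (52%) | 1.47 (99%) | 1.58 (100%) |
| Scan-rate ratio 2, random scans | 1.37 (80%) | 1.18 (29%) | 1.33 (88%) | 1.02 (5%) |
| Scan-rate ratio 2, disease-triggered scans | 1.08 (12%) | 0.81 (41%) | 1.07 (12%) | 0.82 (63%) |

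In the last row, 80% of new M1 cases trigger a scan and background scans run at 0.5/yr. For a death-linked factor, Cox to end of M0 follow-up stays at 1.00 because death removes men from risk without changing the rate of positive scans among those who remain. For a scan-linked factor, neither censoring rule is safe in both settings.

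**Step 4: scan-level simulation** (500 runs, logistic with patient-clustered standard errors, scans up to the first positive, no M1 effect). Drift rows give the OR per SD.

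| Predictor | As written | Post-baseline only | Post-baseline plus log time since last negative scan or baseline |
|---|---|---|---|
| Drift 0.1 SD/yr | 1.10 (57%) | 1.05 (19%) | 1.00 (4–5%) |
| Drift 0.25 SD/yr | 1.25 (100%) | 1.12 (64%) | 1.00 (4–5%) |
| Drift 0.5 SD/yr | 1.42 (100%) | 1.20 (99%) | 1.01 (4–5%) |
| Fixed factor, scan-rate ratio 2, random scans | 0.75 (87%) | 0.61 (100%) | 1.00 (4%) |

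Dropping baseline scans alone is not enough, and for the fixed factor it makes matters worse; the two changes belong together. With disease-triggered scans, the fixed factor goes from about 0.73 as written to about 0.60 after both changes, so the correction does not rescue that case.

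**The case against.** The strongest reply is that the objective in Section 3.2 asks what predicts a later positive scan, and a man who dies first never has one. On that reading an OR of 0.70 at death HR 3 is correct. The reply stands: without dropout, 4-year cumulative incidence in the same setting is about 30% against 39%, an OR of 0.69. The logistic result misleads only as a statement about the M1 rate among men still alive and at risk, which is what the Section 1.2 aim on timing of imaging needs.

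The large figures also need strong links. At death HR 1.3 the OR is about 0.94, with rejection near 7%. With M1 HR 1.5 and death HR 1.5, logistic power is still 90%. That limits the size, not the direction.

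A reader might infer four stronger things that the documents do not support.
- That unequal follow-up by itself creates false predictors. It does not: with no link to the predictor, all four models hold 5–6%.
- That the plan ignores time. It does not: Cox regression is already planned, and Section 8.3.3 adds a Cox analysis of metastasis-free survival with a time origin and censoring date. That rule cannot be carried over whole, because death is an event there.
- That the sponsor meant to pool baseline scans. The text never names them, and post-baseline scans may have been intended. Section 8.3.3 does, however, also model a positive baseline scan in the M0 population, where none can occur, so intent cannot be assumed.
- That Cox regression cures the problem. The scan-linked rows show that it does not.

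The unstated coding of never-scanned men and the missing censoring rule for the Cox model are mainly absent detail. No formal hypothesis rests on this analysis (Section 8.2.2).

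**Conclusion.** The point holds at moderate weight and should be fixed. The scan-level defect is the firmer part: as worded, the data set includes records that cannot be positive, and a null predictor with an assumed drift of 0.25 SD/yr shows an OR of about 1.25. The patient-level part is conditional. It affects only predictors linked to death, dropout or scan frequency, with ORs of about 0.94, 0.83 and 0.70 at assumed death HRs of 1.3, 2 and 3 for a factor with no M1 effect. For death-linked factors it is misleading only for guidance on men still at risk. All rates are assumptions, since the documents give none. The primary endpoint is untouched; the damage is to a secondary predictor list, its effect sizes and any probability quoted from it.

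**What to change.** 1. In the scan-level model, limit the data to post-baseline imaging studies and add time since the last negative (or baseline) scan as a covariate. Make both changes together.
2. Lead with the Cox model already planned: cause-specific, from baseline imaging to first positive scan, with death censored as a competing event. Keep the yes/no logistic model as a sensitivity analysis, state how never-scanned men are coded, and report their number. Show the Cox results under censoring at end of M0 follow-up and at last negative scan, as a sensitivity comparison. Do not turn agreement of the two into a decision rule: with death HR 3 and scan-rate ratio 2 acting together, such a rule gave 17% false positives.
3. Give any predicted probability as cumulative incidence of a positive scan at a stated time, with death as a competing event.
4. Apply the same to the post-baseline analyses in Section 8.3.3, where Cox is planned for biomarkers but only logistic regression for imaging modalities.

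The cost is mostly wording: one extra Cox run, one covariate and one cumulative-incidence estimate, with no new data, since survival status and imaging are already collected. The downsides should be stated. Results become hazard ratios. Never-scanned men (about 10% at one scan per year, 24% at 0.5) contribute no time under last-negative-scan censoring. Bias from discretionary or disease-triggered scanning remains under every model, including the corrected scan-level model.
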